There will be a single subject group in this study. All subjects will receive the active study procedure with the green and violet diodes of the Erchonia® GVL emitted simultaneously.

Comparative subject data for Erchonia® EVRL emitting the red and violet diodes simultaneously will be taken from the 2019 study whose results supported FDA market clearance for K191257.

BLINDING

As all subjects in this study will receive the active procedure administration with the Erchonia® GVL, neither subjects nor investigators will be blinded. The statistician analyzing the study results will however be blinded with respect to study success analysis. The data from this current GVL study and the retrospective data from the 2019 EVRL study will be deidentified and presented to the study statistician as 'Group A' and 'Group B'. The statistician will not be aware of which group – A or B – contains the current GVL study data and which contains the retrospective comparative EVRL study data.

RANDOMIZATION

As this study is a single treatment group study, randomization to procedure group is not applicable. Therefore, this is a non-randomized trial.

SUBJECTS

Subject Sample

Subjects will be males and females 18 years or older who present with chronic (30 consecutive days or longer) neck and/or shoulder pain diagnosed as being of musculoskeletal origin (osteoarthritis, chronic muscle spasm, cervical and thoracic spine sprain strain).

Sample Size

There will be 43 qualified subjects enrolled in this study.

Rationale for Sample Size

Sample size is determined to be identical to that intended to be enrolled in the comparative reference EVRL study.

Recruitment

Subjects may be recruited from among:

- (i) The Principal Investigator's/test site's pool of existing and new patients
- (ii) Referrals from other suitable medical clinics and professionals
- (iii) Subjects who respond to the following recruitment materials:

a) Flyer

WANTED

**ADULTS WITH NECK AND SHOULDER PAIN
ONGOING FOR THE LAST 30 DAYS FOR A
CLINICAL STUDY OF THE EFFECTS OF
LOW LEVEL LASER LIGHT ON
REDUCING NECK AND SHOULDER PAIN**

**THIS STUDY INVOLVES A SINGLE
LASER LIGHT PROCEDURE
WITH THE ERCHONIA® GVL LASER
AT THE TEST SITE**

FOR MORE INFORMATION PLEASE CONTACT:

<PI name>
<test site name & location>
<phone # and/or e-mail>

b) Newspaper Ad

Neck and Shoulder Pain Research Study

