24 HOURS AND 48 HOURS POST-PROCEDURE EVALUATIONS

The subject will be required to record the following at home on the forms provided by the test site at 24 hours and again at 48 hours after completion of the procedure administration phase at the test site.

OUTCOME ASSESSMENTS

- Visual Analog Scale (VAS) Degree of Pain Rating
- Linear Range of Motion (ROM)
- Subject Satisfaction with Study Outcome Rating
- Adverse Events Evaluation

ADVERSE EVENTS

At each evaluation point throughout the clinical study, and at any other time throughout the duration of the clinical trial that is necessary, any and all potential adverse events reported by a subject or observed by an investigator will be recorded on the case report form, and subsequently evaluated by a suitably qualified independent reviewer for determination of relationship to the study treatment and whether or not any corrective action needs to be taken. All potential adverse events recorded will be appropriately reported to the governing IRB, as applicable.

It is unlikely and not expected that any adverse events will result from implementation of this clinical study protocol. Prior clinical trials using low level laser light have not typically yielded any adverse events or reactions. However, potential adverse events that may feasibly occur from application of the Erchonia® GVL include, but are not necessarily limited to: skin irritation, discoloring, rash, indentations and infection.

PRIVACY AND CONFIDENTIALITY

Records for each subject in this clinical study will be maintained in separate files in a locked filing cabinet at the respective test site. The investigator at the test site will be responsible for ensuring that all records for a subject pertaining to his or her participation in the clinical study are stored in that subject's file at all times other than when information is being recorded on them.

Copies of all of the subject case report forms will be made and supplied to Regulatory Insight, Inc. and Erchonia Corporation. Regulatory Insight, Inc. and Erchonia Corporation will maintain these copies in a separate clinical study file that is kept in a locked filing cabinet at their respective premises. The original records will be maintained at the respective test sites.

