- A t-test for two independent sample will be performed to evaluate the significance of the difference in the mean change in VAS pain scores from baseline to endpoint evaluation between the two study groups (GVL vs EVRL) to evaluate for equivalency to support the support the conclusion of the proportion of successes evaluation. Significance levels will be considered at the p<0.05 level.

SECONDARY EVALUATIONS

The following secondary evaluations will be performed on the GVL study data set. As no claims are intended to be made based on the secondary measures, the findings are presented through descriptive analysis and qualitative trending only, without evaluation for or claims of statistical significance.

- Change in mean VAS ratings across study duration: all study evaluation points (baseline, endpoint, 24 hours and 48 hours post-procedure).
- Change in linear ROM measurements across respective study evaluation points at study baseline and endpoint.
- Subject satisfaction with study outcome ratings across study duration.

INDIVIDUAL TEST SITES

Results will be presented by individual test site for comparison.

INDIVIDUAL SUBJECT RESULTS

Individual subject results for study outcome measures will also be presented.

SAFETY ANALYSES

Safety analyses will be based on all enrolled subjects and will be assessed by evaluating and comparing frequency and incidence of observed and/or reported adverse events between subjects in the GVL and the EVRL studies. A chi-square test with a continuity correction will be performed to compare the percentage of subjects who had adverse events between the two subject groups.

INFORMED CONSENT

- Informed consent will be an agreement between the individual investigator and each subject, having the capacity to understand and make an informed decision. Consent will be obtained prior to each potential subject's participation in this clinical study.
- Each subject participating in this clinical study will be made aware of the fact that his or her participation involves research and the intent of the research, the expected duration of his or her participation and a description of the procedures that will be followed.
- Each subject will be made aware of the reasonably expected benefits he or she might receive, as well as any risks or potential discomfort that are involved.
- Each subject will also be made aware of alternative treatments available to him or her.

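### The planned adverse-event test cannot be computed if neither study has an event and is far too conservative with few; exact confidence intervals would say more, at almost no cost

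*Combined protocol and SAP*

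**What the plan says.** The safety analysis is set out in two sentences under Safety Analyses in the statistical analysis plan. The first fixes the population ("Safety analyses will be based on all enrolled subjects") and provides for comparing the frequency and incidence of adverse events between the GVL and EVRL studies. The second names the only inferential method: "A chi-square test with a continuity correction will be performed to compare the percentage of subjects who had adverse events". The plan gives no significance level for this test, no confidence interval, and no rule for a sparse or empty table.

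The Adverse Events section states what the sponsor anticipates: "It is unlikely and not expected that any adverse events will result from implementation of this clinical study protocol". On earlier experience it adds: "Prior clinical trials using low level laser light have not typically yielded any adverse events or reactions".

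Under Sample Size: "There will be 43 qualified subjects enrolled in this study". The rationale is: "Sample size is determined to be identical to that intended to be enrolled in the comparative reference EVRL study". The document gives neither the number actually enrolled in the EVRL study nor that study's adverse-event count.

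**The concern.** A chi-square test, corrected or not, relies on a large-sample approximation that needs a reasonable number of events. The plan pairs it with an expectation of almost none. Two things follow. If both studies are free of events, the expected counts in the event cells are zero and there is nothing to compute. If there are a few events, the continuity correction makes the test very reluctant to reject. In a safety comparison that is the unfavourable direction, because an excess on the new device is more easily labelled non-significant.

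The practical risk lies in the wording of the report. The study is meant to support a 510(k) submission. A missing or non-significant p-value invites a bare statement of no difference, which does not tell the reader how large an event rate the data still allow.

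**Working it through.** **Inputs.** GVL n = 43 (Sample Size). EVRL n = 43 is assumed, since only the intended number is given. Two-sided alpha 0.05 is assumed: the level "Significance levels will be considered at the p<0.05 level" is stated for the efficacy tests, and none is stated for safety. Event rates of 0.5% to 10% are assumed, because the documents give no figure. The plan has no safety calculation of its own to reproduce.

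**1. Empty table.** Write a and b for subjects with an event out of 43 in each group. The expected event count per group is (a + b) × 43/86 = (a + b)/2. With a = b = 0 this is zero and the statistic is 0/0. The probability of no events in 86 subjects is (1 − p)^86:

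| True rate p, both groups | P(no events) |
|---|---|
| 0.5% | 0.995^86 = 0.650 |
| 1% | 0.99^86 = 0.421 |
| 2% | 0.98^86 = 0.176 |
| 5% | 0.95^86 = 0.012 |

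**2. Sparse table.** (a + b)/2 is below 5 whenever a + b is below 10. At a 5% rate, P(fewer than 10 of 86) = 0.989; at 10% it is 0.643. If EVRL had 40 subjects (assumed), the smaller expected count is (a + b) × 40/83, still below 5 with up to 10 events. If it had 86 (assumed), it is (a + b) × 43/129, below 5 with up to 14 events. The conclusion does not depend on the comparator being exactly 43.

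**3. p-values at 43 v 43.** The corrected statistic is 86 × (|43a − 43b| − 43)² / [(a + b)(86 − a − b) × 43 × 43].

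- 5 v 0: 86 × (215 − 43)² / (5 × 81 × 1849) = 3.40, p = 0.065.
- 6 v 0: 86 × (258 − 43)² / (6 × 80 × 1849) = 4.48, p = 0.034.

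Boschloo's test is taken here as unconditional exact, ordering tables by the two-sided Fisher p-value and maximised over the common rate.

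| Events | Corrected chi-square | Fisher | Boschloo |
|---|---|---|---|
| 0 v 0 | undefined | 1.000 | 1.000 |
| 3 v 0 | 0.240 | 0.241 | 0.169 |
| 4 v 0 | 0.125 | 0.116 | 0.075 |
| 5 v 0 | 0.065 | 0.055 | 0.040 |
| 6 v 0 | 0.034 | 0.026 | 0.016 |

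**4. True size and power.** These sum binomial probabilities over all 43 v 43 tables with p < 0.05, counting 0 v 0 as no rejection.

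| Rates | Corrected chi-square | Fisher |
|---|---|---|
| 2% in both (size) | 0.0002 | 0.0002 |
| 5% in both (size) | 0.0049 | 0.0050 |
| 10% in both (size) | 0.015 | 0.019 |
| 10% v 1% (power) | 0.184 | 0.185 |

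The planned test would miss a tenfold excess (10% against 1%) about four times in five.

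**5. What an interval would say.** With 0 of 43, the exact two-sided 95% upper limit solves (1 − p)^43 = 0.025, so p = 1 − 0.025^(1/43) = 0.082. A study with no events has not ruled out a true rate of 8.2%.

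**The case against.** The strongest reply is that little hangs on this test, and that is largely right. Study success is the VAS responder rule. No safety threshold or hypothesis uses the chi-square. The comparator is historical and not randomised, so a p-value just above or below 0.05 would settle nothing. The plan also compares frequency and incidence in its own right, and every potential event goes to an independent reviewer for relationship to treatment.

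Three stronger readings are tempting, and the documents do not support them.

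- **That Fisher's exact test would cure the conservatism.** At 43 v 43 it does not. Size and power are almost the same, and both tests need 6 v 0 to reach p < 0.05 when one group has no events. At 0 v 0 Fisher returns 1.000, which is defined but carries no information. Fisher departs further from the corrected chi-square with unequal groups (3 v 0 at 43 v 86: 0.063 corrected, 0.035 Fisher), but 86 is an assumption.
- **That the plan yields no safety result if there are no events.** Only the p-value is lost; counts and incidence remain. The test is undefined only if both studies are free of events, and the EVRL count is not in the document.
- **That the EVRL group cannot have been 43 because its success rate is given as 75%.** The nearest attainable proportions are 32/43 = 74.4% and 33/43 = 76.7%, but the plan states neither a denominator nor a rounding rule for the 75%. An efficacy proportion also does not fix the number enrolled, which is the safety denominator.

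What remains after these concessions is that the named method does not suit the data the plan anticipates, and that no interval is planned.

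**Conclusion.** The point holds as a minor matter of method and reporting. If both studies have zero events the planned statistic does not exist, whatever the EVRL sample size. With few events at 43 v 43, the test runs at about a tenth of its nominal size for a 5% rate (0.0049/0.05 ≈ 0.10) and far below that for lower rates. Either way the result says little about safety.

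The size and power figures assume 43 EVRL subjects and a two-sided 0.05 level. The probabilities of an empty table also assume the same true rate in both studies. The 8.2% limit needs only the planned GVL enrolment of 43.

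Nothing here affects the efficacy conclusion or the success rule, and it does not suggest that the device is unsafe.

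**What to change.** Replace the chi-square sentence under Safety Analyses with wording to this effect:

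> For each study, the number and percentage of subjects with at least one adverse event will be reported with an exact (Clopper-Pearson) two-sided 95% confidence interval. The difference between studies (GVL minus EVRL) will be reported with an exact unconditional 95% confidence interval. If a study has no events, the upper confidence limit will be reported (8.2% for 0 of 43), and the absence of events will not be described as showing no difference. The comparison is descriptive, because the EVRL data are historical and not randomised.

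If a p-value is still wanted, name an exact test that is defined for sparse tables, and state how its two-sided p-value is formed. Boschloo's test gains over the corrected chi-square (5 v 0: 0.040 against 0.065). Fisher's test is valid but gains almost nothing at equal group sizes. State the enrolled number and the adverse-event count of the EVRL study alongside.

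The cost is a short SAP edit. Data, visits, sample size and the efficacy analysis are unchanged. An exact unconditional interval needs suitable software, but no new information.

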APPENDIX A

LETTER OF APPLICATION FOR NON-SIGNIFICANT RISK (NSR) DETERMINATION

ERCHONIA CORPORATION
LETTER OF APPLICATION FOR NONSIGNIFICANT RISK DETERMINATION
FOR THE ERCHONIA® GVL LASER DEVICE
FOR REDUCING NECK AND SHOULDER PAIN
CLINICAL STUDY V1.0 07.31.20

NAME OF THE DEVICE: Erchonia® GVL

INVESTIGATIONAL INDICATION: The purpose of this clinical study is to determine the effectiveness of the Erchonia® GVL (manufactured by Erchonia Corporation (the Company), when both the green and violet diodes are activated simultaneously, in providing temporary relief of minor chronic neck and shoulder pain of musculoskeletal origin.

REGULATORY BACKGROUND

Erchonia demonstrated the effectiveness of low-level lasers in providing temporary relief of minor chronic neck and shoulder pain of musculoskeletal origin in the following studies, each of which successfully supported FDA 510(k) clearances:

The Erchonia® PL2000, a red (635 nm) diode laser was evaluated for adjunctive use in providing temporary relief of minor chronic neck and shoulder pain of musculoskeletal origin in a double-blinded, sham-controlled, randomized clinical trial, the results of which successfully supported an FDA clearance under K012580 for the following indication:

“The TUCO Erchonia PL2000 is indicated for adjunctive use in providing temporary relief of minor chronic neck and shoulder pain of musculoskeletal origin.”

The TUCO Erchonia PL2000 was subsequently renamed the Erchonia EVRL, and its indications updated under K152196 to include both the treatment of neck and shoulder pain as well as acne vulgaris, as follows:

“The Erchonia EVRL Laser is generally indicated:

- a. while using the red diode, for adjunctive use in providing temporary relief of minor chronic neck and shoulder pain of musculoskeletal origin, and
- b. while using the blue diode, to treat dermatological conditions, and specifically indicated to treat moderate inflammatory Acne Vulgaris”

A non-inferiority study evaluating the Erchonia® EVRL laser employing dual red (635 nm) and violet (405 nm) diodes simultaneously yielded comparable (equivalent) results to the use of red diodes alone for adjunctive use in providing temporary relief of minor chronic neck and shoulder pain of musculoskeletal origin. The results of that clinical study successfully supported FDA clearance under K191257 for the following indication:

“The Erchonia EVRL Laser is generally indicated using the red and violet diode simultaneously, for adjunctive use in providing temporary relief of minor chronic neck and shoulder pain of musculoskeletal origin”

The present study evaluated efficacy of the Erchonia® GVL, a dual diode laser emitting green (520 nm) and violet (405 nm) diodes simultaneously for adjunctive use in providing temporary relief of minor chronic neck and shoulder pain of musculoskeletal origin.

DEVICE DESCRIPTION & DETAILS

The Erchonia® GVL Laser used in this study is a hand held low level laser that uses two semiconductor diodes; a 520 nanometer (visible green light) and a 405 nanometer (visible violet light), each emitting its wavelength with a tolerance of ± 10 nanometer. The lasers are powered by an internal battery that is recharged using a separate inductive charging base powered by an external class II medical power supply. This configuration offers portability as well as consistency of power. The Erchonia® GVL is a variable hertz device. The variable hertz feature of the Erchonia® GVL is a pulsed wave, defined as containing a selected series of breaks, variances that are preprogrammed.

The internal battery powers the two specially created and patented electronic diodes with an output of 7.5mW green ± 1 mW and <5 mW violet laser.

The device contains software that is embedded in a RAM chip on the PCB. This data includes the touch screen images (GUI) and the command prompts that activate the screen icons; work in conjunction with the component platform to ensure the device operates as intended. The exterior materials consist of 6061 T6 AL and Copolymer Acetal with powder coating finish.

The Erchonia® GVL has the following specifications:

Device

- Weight: Laser-.95lbs / .42kgs. Charger Base-.55lbs / .42kgs
- Full Color TFT Touch Screen Module
- Machined billet aluminum enclosure
- Dimensions: Laser-Length-6.9" (17.52cm) Width-3.10" (7.87cm) Depth-.76" (1.93cm), Charger Base- Length-5.7" (14.47cm) Width-3.5" (8.88cm) Depth-1.65" (4.19cm)

Laser

- 2 electronic diodes, with patented optics
- Output: 520 nm 7.5mW (green)
- Output: 405 nm <5 mW (violet)
- Wavelengths: 520 nm & 405nm +/- 10nm
- Duty Cycle: 50%

Power

- Battery: Lithium-ion Polymer 3.7V, 1500mAh, 5.6w

Inductive Charging Base

- 1.5A 12V

External Power Supply

- Model: ER-E-00182
- 100-240Vac, 50-60Hz, 0.5A; 12Vdc 1.5A

Dosage calculations for the Erchonia® GVL

Total energy per diode:

- (diode output means) $mW / 1000$ (converting mW to W) * (time in seconds) $\div 2$ (50% duty cycle) = (total energy per diode per minute)
- 520 nm diode (green): $7.5 / 1000 * 60 \div 2 = .225J$
- 405 nm diode (violet): $4.5 / 1000 * 60 \div 2 = .135J$
- Total device diodes energy per minute: $.36J$
- The Erchonia® GVL used in this study is shown in Figure 1 below.

Figure 1

The following diagram identifies each component of the device and a complete description of the component follows.

Figure 2

#1 POWER BUTTON (ON/OFF)

The Power Button allows you to turn the device ON “I” or OFF “O”. To turn the device ON, press and Hold this button, after approximately 3 seconds the green (#2 Power On Light) turns on. To turn off the device it is recommended to use the “**Powering Down**” method, explained in the **Operation Section** of the manual. In the unlikely event that your device stops responding to

touches, by pressing and holding the power button for 15 seconds will force shut down the device. This is only recommended if the device cannot be turned off from the “**Powering Down**” method.

#2 LASERS ON LIGHT

The “Lasers On” light is an LED indicator that will light up when the Lasers are ON and turn off when the lasers are OFF.

#3 POWER ON LIGHT

The “Power On” light is an LED indicator that will display a constant green light when the device is powered on and turn off only when the device is OFF.

#4 TOUCH SCREEN

The touch screen functions as a display screen and an input panel, providing information and a means to operate the device by touching the appropriate icon.

#5 PIVOTING LASER MOUNT

The Pivoting Laser Mount allows you to adjust the laser angle (up to 20° each direction) based on your preference.

#6 LASER DIODES

The Lasers consist of two electronic laser diodes, with patented optics. These laser diodes when activated by the internal power source generate laser energy thereby emitting on one side a red beam and the other side a violet beam. This is a specially designed and patented device created to ensure the laser beam is focused and directed for the most optimal use. The device can be programmed with up to 4 defined Hz frequencies (two for each diode).

CHARGER BASE

[figure not shown]

Figure 3

POWER SUPPLY

Figure 4

#1 INDUCTIVE CHARGER BASE

The Inductive Charger Base is a custom based system specifically designed to charge the laser device. It is an inductive charging system that charges the device wirelessly. The Charger Base must be plugged into the power supply and the power supply must be plugged into a wall socket for Charger Base to receive power. Once powered up, the Laser device is placed on Charger Base with the touch screen facing up and Laser diodes facing away from Charger Base LED lights.

#2 CHARGER BASE POWER LIGHT

The Charger Base “Power” Light is the power indicator LED that will light up when the energized Power Supply connector is plugged into the Inductive Charger Base.

#3 DOCKED LIGHT

The “Docked” light is an indicator LED that will light up to indicate the device is correctly docked in the inductive charger base. The LED will flash ON and OFF when correctly in place and turn off when removed from the inductive charger base.

#4 CHARGER BASE CONNECTOR PORT

The Charger Base Connector Port is the location to plug the Power Supply Connector in to supply power to the inductive charger base.

#5 POWER SUPPLY CONNECTOR

The Power Supply Connector plugs into the Inductive Charger Base Connector Port to provide power to charger base.

DEVICE SAFETY

RISK AND PREVENTION OF EYE INJURY

The Erchonia® GVL is classified by the FDA/IEC as a Class 2 laser device. This designation represents a current standard for use in order to ensure the safety of the subject. A Class 2 laser is determined to have a chronic viewing hazard. Pointing the laser beam directly into the eye and maintaining it there for an extended period of time could prove to be damaging.

To ensure there is no possible instance of residual effect, eye protection is implemented for the subject receiving the laser procedure administrations.

A pair of safety glasses is provided for use during all procedure applications. These safety glasses are Noir laser shields. The safety glasses sufficiently and effectively block the laser light spectrum at OD 6+ @ 190-534nm, OD 1.5+ @ 620-650 nm, VLT 7%.

- Height: 47 mm
- Width: 130 mm
- Length: 130 mm

E

FOOD AND DRUG ADMINISTRATION (FDA) DETERMINATION OF NON-SIGNIFICANT RISK (NSR) STATUS

(i) Regulatory Clearances: The Food and Drug Administration (FDA) has determined the family of Erchonia® low level laser devices, including those employing 520 nm green diodes and 405 nm blue/violet diodes, to be non-significant risk (NSR) through numerous **510(k) clearances**, including several for pain relief indications, as follows.

- 1. K132940:** *Erchonia® Allay™*: is indicated as an adjunct to reducing chronic heel pain arising from plantar fasciitis.
- 2. K072206:** *Erchonia® EML Laser*: is indicated for the temporary reduction in post-surgery pain at 24 hours after surgery following bilateral breast augmentation surgery.
- 3. K050672:** *Erchonia® EVRL Laser*: The Erchonia EVRL Laser is generally indicated:
 - a. while using the red diode, for adjunctive use in providing temporary relief of minor chronic neck and shoulder pain of musculoskeletal origin, and
 - b. while using the blue diode, to treat dermatological conditions, and specifically indicated to treat moderate inflammatory Acne Vulgaris.
- 4. K041139:** *Erchonia® EML Laser*: is indicated as an adjunct to liposuction procedures of the thighs, hips and stomach for reduction of pain associated with the recovery process.
- 5. K100509 & K130741:** *Erchonia® THL1 Laser & Erchonia® PL5000*: is indicated for adjunctive use in providing temporary relief of minor chronic neck and shoulder pain of musculoskeletal origin.
- 6. K130996:** *Erchonia® XLR8™*: The Erchonia XLR8™ is indicated for the following three indications:
 - a. adjunctive use in providing temporary relief of minor chronic neck and shoulder pain of musculoskeletal origin
 - b. as an adjunct to liposuction procedures of the thighs, hips and stomach for reduction of pain associated with the recovery process
 - c. temporary reduction in post-surgery pain at 24 hours after surgery following bilateral breast augmentation surgery
- 7. K142042:** *Erchonia® SHL Laser*: is indicated for use as a non-invasive dermatological aesthetic treatment for reduction of circumference of hips, waist and upper abdomen when applied to individuals with a Body Mass Index (BMI) between 30 kg/m² and 40 kg/m².
- 8. K130922:** *Erchonia® Verju Laser System with Massager*: is indicated for use as a non-invasive dermatological aesthetic treatment as an adjunct for individuals intending to undergo liposuction procedures for the reduction of circumference of hips, waist and thighs. The Massager component is indicated for the temporary reduction in the appearance of cellulite.
- 9. K123237 & K133718:** *Erchonia® Zerona™ 2.0 Laser & Zerona®-Z6*: is indicated for use as a non-invasive dermatological aesthetic treatment as an adjunct for individuals intending to undergo liposuction procedures for the reduction of circumference of hips, waist, and thighs.
- 10. K121695 & K082609:** *Erchonia® ML Scanner (MLS) & Erchonia® Zerona*: is indicated for use as a non-invasive dermatological aesthetic treatment as an adjunct for individuals intending to undergo liposuction procedures for the reduction of circumference of hips, waist, and thighs.
- 11. K21690 & K120257:** *Erchonia® MLS, Zerona, Zerona-AD*: is indicated for use as a non-invasive dermatological aesthetic treatment as an adjunct for individuals intending to undergo liposuction procedures for the reduction of circumference of the upper arms.

12. K101430: MLS-AC Derma Scanner™: is indicated while using the red diodes for adjunctive use in providing temporary relief of minor chronic neck and shoulder pain of musculoskeletal origin, and while using the blue diode, to treat moderate inflammatory Acne Vulgaris.

13. K082609: Erchonia® ML Scanner (MLS): is indicated for use as a non-invasive dermatological aesthetic treatment for the reduction of circumference of hips, waist and thighs.

14. K191257: Erchonia EVRL is indicated while using the red and violet diode simultaneously, for adjunctive use in providing temporary relief of minor chronic neck and shoulder pain of musculoskeletal origin

(iii) **Pre-IDE Reviews:** FDA has previously reviewed numerous clinical study protocols employing various Erchonia® Corporation low level laser devices, including all of the clinical studies conducted in support of the above 510(k) clearances. For all of the FDA's pre-IDE reviews of Erchonia low level laser clinical study protocols, there was concurrence from FDA that the clinical study protocols and application of the Erchonia laser devices therein were considered non-significant risk (NSR).

INSTITUTIONAL REVIEW BOARD (IRB) DETERMINATION OF NON-SIGNIFICANT RISK (NSR) STATUS

Erchonia® Corporation low level laser devices have been determined to be non-significant risk (NSR) when applied in various clinical studies through several IRBs and application for pain reduction indications, as follows:

- Western Institutional Review Board (WIRB®) has previously determined Erchonia low level laser devices to be non-significant risk (NSR) when applied in the following clinical studies:
 1. **WIRB PRO NUM: 20121548:** Erchonia® MLS: A double-blind, placebo-controlled randomized evaluation of the effect of the Erchonia® ML Scanner (MLS) laser on reducing pain associated with degenerative arthritis (osteoarthritis) of the midfoot clinical study protocol
 2. **WIRB PRO NUM: 20120787:** Erchonia® MLS: A double-blind, placebo-controlled randomized evaluation of the effect of the Erchonia® ML Scanner (MLS) on low back pain clinical study protocol
 3. **WIRB PRO NUM: 20111793:** Erchonia® MLS: A double-blind, placebo-controlled randomized evaluation of the effect of the Erchonia® ML Scanner (MLS) laser on chronic heel pain clinical study protocol
 4. **WIRB PRO NUM: 20110331:** Erchonia® MLS: An evaluation of the effectiveness of the Erchonia® ML Scanner (MLS) as a non-invasive dermatological aesthetic treatment for the reduction of circumference of the upper arms clinical study protocol
 5. **WIRB PRO NUM: 20120911:** Erchonia® MLS: A double-blind, placebo-controlled randomized evaluation of the effect of the Erchonia® ML Scanner (MLS) on body contouring of the waist, hips and thighs five-day treatment protocol clinical study protocol

6. **WIRB PRO NUM: 20110758:** Erchonia® MLS: A pilot evaluation of the effect of the Erchonia® ML Scanner (MLS) laser device on enhancing body weight loss, fat loss and circumference reduction of the waist, hips and thighs clinical study protocol
7. **WIRB PRO NUM: 20121330:** Erchonia LUNULA™: An Evaluation of the Effect of the Erchonia LUNULA™ on Treating Toenail Onychomycosis Clinical Study Protocol; Version 6.0 August 7, 2012
8. **WIRB PRO NUM: 20110461:** Erchonia FX-405™: An Evaluation of the Effect of the Erchonia FX-405™ on Treating Toenail Onychomycosis Clinical Study Protocol; Version 3.0 March 19, 2011
9. **WIRB PRO NUM: 20120489:** Erchonia® MLS: A double-blind, placebo-controlled randomized evaluation of the effect of the Erchonia® ML Scanner (MLS) on lipid panel levels clinical study protocol.
10. **WIRB PRO NUM: 20180778:** Erchonia® EVRL: An Evaluation of the effect of the Erchonia® EVRL on Neck and Shoulder Pain

➤ Independent Review Consulting, Inc.'s/Ethical and Independent Review Services has previously determined Erchonia low level laser devices to be non-significant risk (NSR) when applied in the following clinical studies:

1. **IRC# 07150, NSR# DER-006:** Erchonia® MLS: A double blind, placebo-controlled randomized evaluation of the effect of the Erchonia® ML Scanner (MLS) on body contouring of the waist, hips and thighs clinical study protocol.
2. **IRC# 09120, NSR# DER-015:** Erchonia® MLS: A double-blind, placebo-controlled randomized evaluation of the effect of the Erchonia® ML Scanner (MLS) on reducing the appearance of cellulite clinical study protocol.
3. **IRC# 08167, NSR# DER-009:** Erchonia® MLS: A double blind, placebo-controlled randomized evaluation of the effect of the Erchonia® ML Scanner (MLS) on capsular contracture clinical study protocol.
4. **IRC# 09059, NSR# DER-010:** Erchonia® MLS: A double blind, placebo-controlled randomized evaluation of the effect of the Erchonia® ML Scanner (MLS) in combination with silicone sheets on cellulite pilot study protocol.

➤ Chesapeake Research Review, Inc. determined the Erchonia® ML Scanner (MLS) laser device to be a non-significant risk (NSR) device when applied in the following study:

- (i) **Pro. # 00006393:** Erchonia® MLS: A pilot evaluation of the effect of the Erchonia® ML Scanner (MLS) as applied to the abdomen on reducing visceral abdominal fat in patients with HIV-associated lipodystrophy.

OTHER POTENTIAL RISKS

Other potential risks and their mitigation include:

- (i) Electric shock: operator risk only: mitigated through electrical safety testing.
- (ii) Electromagnetic interference: mitigated through EMC/EMI testing.
- (iii) User error: mitigated through instructions for use documentation.

LABELING

The device used in this clinical study shall be labeled with the following statement:

"CAUTION – Investigational device. Limited by United States law to Investigational use."

- Do you contend that this device as used in this protocol is an NSR device?
 Yes No
- Has another IRB decided this device is SR?
 Yes No
- Does this type of device appear as SR on the FDA Information Sheet?
 Yes No
